15.6.2. The Sponsor

The Sponsor's responsibilities include the following:

- Before study site activation and participant enrollment, the Clinical Monitor is responsible for reviewing with study site staff the definitions of AE and SAE, as well as the instructions for monitoring, recording, and reporting AEs and SAEs.
- The Sponsor is to notify all appropriate regulatory authorities, central ethics committees, and Investigators of SAEs, as required by local law, within required time frames.

CONFIDENTIAL

The information contained herein may not be used, disclosed, or published without the written consent of
Biogen MA Inc.

16. STATISTICAL METHODS AND DETERMINATION OF SAMPLE SIZE

The objectives of the study and the endpoints to be analyzed are listed in Section 6.

16.1. Analysis Population

The safety population is defined as participants who enrolled and have received at least 1 dose of study treatment in the extension study. The analyses of clinical function and safety for 233AS102 will be performed for the safety population. Integrated analyses of 233AS101 and 233AS102 will be performed for the populations defined in 233AS101 protocol for mITT and non-mITT.

For participants from Part C of 233AS101 who enrolled in 233AS102, summaries for clinical function, PK, PD/biomarker endpoints, and safety evaluations will also be presented by disease progression subgroup (i.e., those who met prognostic enrichment criteria for rapid disease progression in 233AS101 Part C [labelled as "enriched" for analyses] and all other eligible participants in 233AS101 Part C [labelled as "other"]). Summaries of data collected during 233AS102 for participants from Part C of 233AS101 will be presented by prior treatment group from 233AS101. Integrated summaries of 233AS101 and 233AS102 will be presented by treatment group during 233AS101 for each of the mITT and non-mITT populations, with some limited summaries for overall intention-to-treat population.

Generally, data for participants from 233AS101 Part C will be analyzed separately from that of participants from Parts A and B, but there may be some analyses where all participants in the extension study will be pooled, particularly for safety summaries. Participants from Parts A and B will generally be pooled together; the data in these participants will mainly be grouped overall rather than by dose level, but there may be limited summaries based on individual dose level. Further details will be provided in the interim and/or final statistical analysis plan.

Some of the analyses specified will be more relevant for integrated efficacy, safety, and immunogenicity plans where data from both 233AS101 and 233AS102 will be pooled.

16.2. Clinical Function

16.2.1. Methods of Analysis

As this is an open-label, long-term extension study, analyses will be exploratory and descriptive in nature.

Data will be summarized using descriptive statistics for continuous variables and using frequency and percentage for discrete variables. For participants who have completed Parts A or B of Study 233AS101, the time trajectory of each clinical function may be summarized at selected timepoints and presented in plots. For participants who have completed Part C of Study 233AS101, the time trajectory will be summarized by the prespecified subgroup (enriched population versus other eligible participants) and the prior treatment received during Study

CONFIDENTIAL

The information contained herein may not be used, disclosed, or published without the written consent of Biogen MA Inc.

233AS101 from the baseline of Study 233AS101 (including data from Studies 233AS101 and 233AS102), from the baseline of Study 233AS102 (including data from Study 233AS102 only), and from the start of BIIB067 100 mg dosing.

Efficacy will be measured based on changes in ALSFRS-R, percent predicted SVC, HHD Megascore and individual muscle strength, [REDACTED]. Changes from baseline (using definitions outlined above) will be summarized over time for each of these endpoints.

Analysis of covariance using multiple imputation will be performed at selected timepoints, based on level of data available at interim and final analysis.

Time to death or permanent ventilation (i.e., ≥ 22 hours of mechanical ventilation [invasive or noninvasive] per day for ≥ 21 consecutive days) and time to death will be summarized using Kaplan-Meier curves based on the starting time using the following:

1. Entry into Study 233AS101
2. Entry into Study 233AS102
3. The start of BIIB067 100 mg dosing
4. Time of symptom onset

The relationship between PK or PD endpoints and the clinical function endpoints will also be explored.

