5.1. Overview of Amyotrophic Lateral Sclerosis

ALS is a rare neurodegenerative disease resulting in loss of motor neurons within the cortex, brainstem, and spinal cord. Patients suffer gradual loss of muscle mass, strength, and function in bulbar, respiratory, and voluntary muscle. Decline is inevitable, with death from respiratory failure following 2 to 5 years after diagnosis for most patients. Although the majority of patients suffer from sporadic ALS, a smaller fraction of patients, approximately 2%, have an inherited, or familial, form of ALS caused by a variety of mutations in SOD1 (referred to as SOD1-ALS) [ALSoD 2015; Ferlay 2013]. During the time since SOD1-ALS was first described in 1993, more than 180 SOD1 mutations have been reported to cause this form of ALS. Disease progression for individual mutations is variable, with survival of less than 15 months seen with the most severe mutations [Cudkowicz 1997].

Overexpression of mutant SOD1 in mice or rats recapitulates important aspects of ALS in humans [Brujin and Cleveland 1996; Gurney 1994]; however, loss of SOD1, while resulting in eventual motor neuron dysfunction, does not result in motor neuron death [Fischer 2012; Reaume 1996]. Furthermore, neither loss nor increase of SOD1 activity in mouse models of SOD1-ALS alters survival [Brujin 1998]. In humans, individual disease mutations are associated with varying levels of SOD1 activity; some patients with disease-causing mutations have apparently normal SOD1 activity [Howlader 2015]. Thus, correlation between disease severity and normal SOD1 activity has not been observed [Andersen 1997; Howlader 2015; Ratovitski 1999]. In contrast, reduction of SOD1 with intracerebroventricular-delivered SOD1 ASO extended survival in a rodent model of SOD1-ALS [Smith 2006]. These observations strongly suggest that SOD1-ALS is caused by toxic properties of the mutant SOD1 protein. Reducing SOD1 mRNA and, subsequently, toxic SOD1 protein may offer therapeutic benefit for patients with SOD1-ALS. IT delivery of an ASO targeting SOD1 mRNA is a viable method to reduce toxic SOD1 protein.

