8. SELECTION OF PARTICIPANTS

8.1. Inclusion Criteria

To be eligible to participate in this study, candidates must meet the following eligibility criteria at Screening, or at the time point specified in the individual eligibility criterion listed:

1. Ability of the participant to understand the purpose and risks of the study and indicate consent, and ability of the participant or his/her legally authorized representative to provide signed and dated informed consent and authorization to use PHI in accordance with national and local participant privacy regulations.
2. Must have diagnosis of SOD1-ALS and must have completed the End of Study Visit for either Parts A, B, or C of Study 233AS101 (i.e., were not withdrawn).
3. If taking riluzole, participant must be receiving a stable dose for ≥ 30 days prior to Day 1.
4. If taking edaravone, participant must have initiated edaravone ≥ 60 days (2 treatment cycles) prior to Day 1. Edaravone may not be administered on dosing days during this study.
5. Medically able to undergo the study procedures, and to adhere to the visit schedule at the time of study entry, as determined by the Investigator.
6. Must have screening values of coagulation parameters including platelet count, INR, PT, and aPTT within normal ranges. Coagulation tests may be repeated at the local laboratory once if, in the opinion of the Investigator, values of the initial tests are out of range but deemed not clinically significant. Participants with nonclinically significant and stable out-of-range values may be eligible to enroll in the study at the discretion of the Investigator. (For normal ranges, please refer to the Study Reference Guide).
7. Female participants of childbearing potential must agree to practice effective contraception during the study and be willing and able to continue contraception for 5 months after their last dose of study treatment. For further details of contraceptive requirements for this study, please refer to (see Section 15.5).
8. Participants in Parts A and B must have a washout ≥ 16 weeks between the last dose of study treatment received in Study 233AS101 and the first dose of BIIB067 received in the current Study 233AS102. Participants in Part C do not require a washout period.

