QTc	interval between the start of the QRS complex and the end of the T wave, corrected for heart rate
QTcF	QTc interval using Fridericia's formula
RBC	red blood cell (count)
RNA	ribonucleic acid
RR	inter-beat
SAE	serious adverse event
SAP	statistical analysis plan
SAS	statistical analysis system
SD	standard deviation
SDTM	standard data tabulation model
SE	standard error
[REDACTED]	[REDACTED]
SOC	system organ class
SOD	superoxide dismutase 1
SVC	slow vital capacity
ULN	upper limit of normal
WBC	white blood cell (count)
WHO	World Health Organization
[REDACTED]	[REDACTED]
[REDACTED]	[REDACTED]

1. Introduction

Study 233AS102 is an extension study of 233AS101 to assess the long-term safety, tolerability, pharmacokinetics, pharmacodynamics, and efficacy of BIIB067 administered to previously treated adults with ALS caused by SOD1 mutation, who have completed Parts A, B, or C of Study 233AS101.

Study 233AS101 is a randomized, double-blind, placebo-controlled, 3-part study to examine the efficacy, safety, tolerability, pharmacokinetics (PK), and pharmacodynamics (PD) of BIIB067, administered by intrathecal bolus injection in subjects with ALS and a confirmed SOD1 mutation.

This statistical analysis plan (SAP) is prepared to describe the final analysis for the closeout clinical study report for 233AS102; separate SAPs exist for 233AS101 Parts A and B, 233AS101 Part C, and integrated analyses across the studies. Prior versions of the SAP for 233AS102 (Versions 1.0 to 3.0) were generated for the purpose of interim analyses based on interim data cuts for the study.

BIIB067 will be referred to as tofersen throughout the rest of the statistical analysis plan.

There are limitations for subjects who enrolled from 233AS101 Parts A and B which impact the interpretability of these subjects in 233AS102:

- Subjects who completed Parts A or B of 233AS101 had a significant washout period ranging from 16 weeks to over 2 years from their last dose of study treatment in 233AS101 to their first dose in 233AS102.
- Dosing paradigms varied substantially across subjects as dose levels in 233AS102 were increased over time as additional doses were deemed to have an acceptable safety profile in 233AS101.
- Many subjects had meaningful disease progression during the washout and exposure to lower doses resulting in a large proportion of discontinuations across studies

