There are also some limitations on statistical analysis for subjects who enrolled into 233AS102 from 233AS101 Part C. Some subjects will be tofersen naïve and others will have received approximately 6 months of tofersen treatment prior to entry in 233AS102.

Analyses of efficacy and biomarker endpoints conducted for interim data (July 2021 and January 2022) highlighted the limitations of conducting standalone 233AS102 analyses in these endpoints as outlined below. Based on these learnings, it only makes sense to analyze the longitudinal data from 233AS102 for efficacy and biomarker endpoints as part of an integrated analysis of 233AS101 and 233AS102:

- In contrast to the prespecified integrated analyses of 233AS101 Part C and 233AS102, the standalone analyses of 233AS102 are based on data selected using post-randomization factors and therefore break the original randomization. On the other hand, the overall ITT analysis with the original 233AS101 Part C baseline provides an objective comparison of the two treatment regimens.

- Rate of progression is variable over time. Comparison of the treatment groups from 233AS102 fails to reflect the overall treatment effect due to early tofersen initiation that is evident in 233AS101 Part C. For example, if rate of progression is faster for the delayed start group in period 1 and then becomes comparable to the early start group, the comparison using only period 2 data would be misleading.
- There are imbalances at baseline of 233AS102, as expected due to the effect of tofersen in 233AS101 Part C, thus confounding interpretation of 233AS102 analyses.
- As described above, incorporation of baseline NfL as a covariate is the most objective mechanism to control for disease heterogeneity at baseline. However, baseline neurofilament in 233AS102 cannot be incorporated as a covariate due to the confounding effect of tofersen administration during 233AS102.

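### Kaplan-Meier curves from symptom onset have no delayed-entry rule, so survival from onset would be overstated unless the ISE SAP supplies one

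*Protocol*

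**What the plan says.** Protocol 16.2.1 states that the two time-to-event endpoints "will be summarized using Kaplan-Meier curves based on the starting time using the following". It then lists entry into 233AS101, entry into 233AS102, the start of 100 mg dosing, and "Time of symptom onset". Both endpoints are secondary (Protocol 6.2.4), and 16.2.1 describes the analyses as exploratory and descriptive. Neither document mentions delayed entry, left truncation or a rule for entering the risk set.

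On populations, Protocol 16.1 says: "The analyses of clinical function and safety for 233AS102 will be performed for the safety population". It adds: "Integrated analyses of 233AS101 and 233AS102 will be performed for the populations defined in 233AS101 protocol for mITT and non-mITT". Under Protocol 8.1, extension participants "must have completed the End of Study Visit for either Parts A, B, or C of Study 233AS101".

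The final SAP moves efficacy out of the 233AS102 report. SAP 4.8.1 drops analysis from the 233AS102 baseline, and SAP 5 leaves other baseline definitions to the ISE SAP. On the integrated data, SAP 1 argues that "the overall ITT analysis with the original 233AS101 Part C baseline provides an objective comparison of the two treatment regimens".

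**The concern.** A participant is in the data only if alive at 233AS101 entry. Between onset and that entry nobody in the data set can be seen to die. An ordinary curve from onset still treats everyone as at risk throughout that interval, so it credits the cohort with survival that was a condition of being observed.

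Choosing a broader population does not cure this. Including everyone dosed in 233AS101 removes selection on finishing that study, but the onset curve remains truncated at 233AS101 entry.

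Survival from onset is easily set beside outside survival figures, and in an open-label study an inflated curve would look like benefit. The people most easily missed are those who die quickly. Protocol 5.1 says of them: "Disease progression for individual mutations is variable, with survival of less than 15 months seen with the most severe mutations".

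**Working it through.** The plan states no median, survival rate or event count for these curves, so there is no figure to reproduce. What can be checked is the direction and plausible size of the error. All hazards and entry times below are assumptions.

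**1. Closed form, fixed delay.** Let survival from onset be Weibull with median m and shape k, S(t) = exp[−ln 2 · (t/m)^k], and let everyone enter d months after onset. The ordinary curve stays at 1 until d and then follows S(t)/S(d). Its median solves t^k = d^k + m^k. With m = 36 and d = 18 (the mean of a uniform 6 to 30 month delay):

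| Shape k | Calculation | Ordinary median | Excess over 36 |
|---|---|---|---|
| 1 (constant hazard) | 18 + 36 | 54.0 | 18.0 |
| 1.5 | (76.4 + 216)^(2/3) | 44.1 | 8.1 |
| 2 | √(324 + 1296) | 40.2 | 4.2 |

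**2. Simulation, entry independent of survival.** True medians were 24, 36 and 60 months. Entry was uniform 6–30, uniform 3–36, gamma (mean 18, SD 12) or lognormal (median 12, log SD 0.7). Only those alive at entry were kept, 200,000 per cell, with censoring 36 to 84 months after entry. The upper limit matches Protocol 7.2: 360 + 4 = 364 weeks, about 84 months.

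- Ordinary curve, excess over the true median: about 13 to 19 months at shape 1, 5 to 10 at shape 1.5 and 3 to 7 at shape 2.
- Delayed entry, constant hazard: 0.3 to 6.1 months above the true median. The remainder arises because the curve cannot start before the earliest entries.
- Delayed entry drawn from month 12 and compared with the true median given survival to month 12: within about 0.4 month.

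A separate case shows the same structure. With constant hazard, true median 36 and entry uniform over 12 to 36 months, the ordinary median is about 60 (24 + 36). Delayed entry gives 47 to 49, against a conditional truth of 12 + 36 = 48.

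**3. Simulation, fast progressors entering sooner.** Fast group: median 15, entry at 6–14 months. Slow group: median 60, entry at 12–48 months.

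| Fast share | True | Ordinary (error) | Pooled delayed entry (error) |
|---|---|---|---|
| 30% | 38.4 | 65.9 (+27.5) | 25.4 (−13.0) |
| 40% | 32.6 | 56.8 (+24.2) | 23.5 (−9.1) |
| 50% | 27.9 | 48.8 (+20.9) | 22.8 (−5.1) |

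Within the two groups at a 40% fast share, delayed entry reads 21 and 73 against conditional truths of 21 and 72; the ordinary curve reads 25 and 90. With graded dependence between entry time and survival, a correlation of 0.25 gives errors of −0.4 to −9 months with delayed entry and about +17 without it. At 0.5 the errors are −7 to −29 and +15 to +17.

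**4. The other early origins, only if limited to people who rolled over.** Take an assumed 0.20 deaths per year and 28 weeks from 233AS101 entry to extension entry in Part C. Two-year survival from 233AS101 entry is exp(−0.20 × 104/52.18) = 0.67. Among extension entrants it would read exp(−0.20 × 76/52.18) = 0.75.

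**The case against.** The strongest reply is that 16.2.1 is silent on delayed entry and does not exclude it. Protocol 16.1 leaves details to SAPs, and the final SAP passes other origins to the ISE SAP. No passage of the SAP mentions an onset curve, so whether one will be run, and how, cannot be seen here. This stands. A reader might infer that the sponsor has decided on an ordinary curve, or that a reported result is already inflated; the documents do not support either. Nor do they cancel the curve: SAP 4.8.1 drops analysis from the 233AS102 baseline, which symptom onset is not.

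The size is also open to challenge. The 13 to 19 month figure needs a constant hazard from the first symptom. A rising hazard is at least as plausible in a progressive disease and cuts the error to single figures in most cases. This stands too, and a single headline figure would mislead. Moreover, 16.2.1 promises curves and does not name a median.

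A third objection is that delayed entry is not always better. Step 3 confirms this for a pooled curve when entry depends on prognosis, which Protocol 5.1 makes plausible. It limits the fix but does not rescue the ordinary curve, which errs upward in every case examined.

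Finally, a reader might extend the criticism to the curves from 233AS101 entry and from the start of 100 mg, or to Parts A and B, who "had a significant washout period ranging from 16 weeks to over 2 years" between studies. The first holds only if those curves were limited to the extension population, and the integrated-analysis wording in Protocol 16.1 and the ITT preference in SAP 1 point the other way. The Parts A/B gap is disclosed in the SAP, and Protocol 16.1 says those participants are generally analysed apart from Part C.

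**Conclusion.** The concern holds in conditional form. As written, 16.2.1 allows an ordinary curve from onset in people selected for having survived to entry. That curve would overstate survival from onset unless the ISE SAP specifies delayed entry. The actual size cannot be computed, because the documents give no onset-to-entry distribution and no hazard shape. For independent entry and true medians of 24 to 60 months, the excess in the median is about 13 to 19 months at constant hazard, 5 to 10 at Weibull shape 1.5 and 3 to 7 at shape 2. It is 21 to 28 months in the two-group case where fast progressors enter sooner.

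The primary endpoint, incidence of AEs and SAEs, is untouched, and no confirmatory result depends on these curves. The matter is worth correcting because the remedy is cheap and the error runs in the drug's favour. Delayed entry does not recover the unconditional median from onset. It estimates survival given survival to the start of the curve, and only if entry time is independent of survival.

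**What to change.** In Protocol 16.2.1, and carried into the ISE SAP:

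- State that any onset-based curve uses left-truncated risk sets, with participants joining at 233AS101 Day 1, or at 233AS102 Day 1 if only extension participants are analysed.
- Show numbers at risk, start the curve at the first time with an adequate risk set (20 is one workable threshold), and label it conditional on survival to that time.
- State the independence assumption, show the curves by mutation or progression class as well, and do not quote a pooled median from onset if dependence is evident.
- If this is not wanted, drop the onset origin.
- As a secondary clarification, state that curves from 233AS101 entry and from the start of 100 mg include everyone who reached that origin, whether or not they rolled over. SAP 3.5 also applies the label ITT to those dosed in 233AS102, so the population should be spelled out.

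The cost is wording plus an entry-time option in the survival procedure. Onset dates are already needed for the SAP 4.3 summaries, and Appendix A gives a rule for partial dates.

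The downside is small early risk sets, wider intervals and a later start. In simulation (true median 36, entry at 6–30 months, at least 20 at risk), the curve starts near month 10 with 183 participants and month 12 with 99, the Part C size. The delayed-entry median then ranges over 36–53 or 35–59 months around conditional targets of about 46 or 48. The ordinary median ranges over 47–62 or 44–66 and would be read as an estimate of 36.

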16.3. Pharmacokinetics

16.3.1. Analysis Population

The PK population is defined as participants who have received at least 1 dose of study treatment and have at least 1 available postdosing evaluation of PK endpoints in the extension study.

16.3.2. Methods of Analysis

Plasma and CSF BIIB067 concentrations will be summarized using descriptive statistics and, where warranted, presented graphically.

16.4. Pharmacodynamics

16.4.1. Analysis Population

The PD population is defined as participants who have received at least 1 dose of study treatment and have at least 1 available postdosing evaluation of the respective PD endpoint in the extension study.

CONFIDENTIAL

The information contained herein may not be used, disclosed, or published without the written consent of Biogen MA Inc.

16.4.2. Methods of Analysis

The PD/biomarker endpoints will be analyzed using similar methods to those used for clinical functions described above in Section 16.2.1. The relationship between PD/biomarker endpoints and clinical functions will be explored using modeling.

